8.6 Definition of End of Study

The end of trial is the date of the last patient last visit (Visit 2).

Each participant will have the right to withdraw from the study at any time. In addition, the investigator may discontinue a participant from the study at any time if the investigator considers it necessary for any reason including:

- Ineligibility (either arising during the study or retrospective having been overlooked at screening)
- Pregnancy
- Significant protocol deviation
- A serious adverse event which requires results in inability to continue to comply with study procedures
- Disease progression which results in inability to continue to comply with study procedures
- Consent withdrawn
- Lost to follow up

The reason for withdrawal will be recorded in the CRF.

8.7 Source Data

In this study a paper CRF will be collected for all 'research only' measurements defined in tables 1 and 2. The electronic CRFs will be used as the source document for the captured data fields described in Table 1 and 2 that are part of routine clinical care. The rationale for this is that data collection for routine clinical care measures within MRC EMBER is populated in to the eCRF from existing UHL IM&T systems (Figure 4 e.g. IMPAX, ilab, CODE BREAKER) as well as prospectively confirmed by the research team for relevant study clinical meta data of interest e.g. smoking status, medication.

9. SAFETY REPORTING

9.1 Definitions

9.1.1 Adverse Event (AE)

An AE or adverse experience is:

Any untoward medical occurrence in a patient or clinical investigation participants, which does not necessarily have to have a causal relationship with this treatment.

An AE can therefore be any unfavourable and unintended sign (including an abnormal laboratory finding), symptom or disease temporally associated with the the study, whether or not considered related to the study.

Page 30 of 46

9.1.2 Adverse Reaction (AR)

All untoward and unintended responses related to the study.

All cases judged by either the reporting medically qualified professional or the sponsor as having a reasonable suspected causal relationship to the study qualify as adverse reactions.

9.1.3 Severe Adverse Events

To ensure no confusion or misunderstanding of the difference between the terms "serious" and "severe", which are not synonymous, the following note of clarification is provided:

The term "severe" is often used to describe the intensity (severity) of a specific event (as in mild, moderate, or severe myocardial infarction); the event itself, however, may be of relatively minor medical significance (such as severe headache). This is not the same as "serious," which is based on patient/event outcome or action criteria usually associated with events that pose a threat to a participant's life or functioning. Seriousness (not severity) serves as a guide for defining regulatory reporting obligations.

9.1.4 Serious Adverse Event or Serious Adverse Reaction

A serious adverse event or reaction is any untoward medical occurrence that:

- Results in death.
- Is life-threatening,

NOTE: The term "life-threatening" in the definition of "serious" refers to an event in which the participant was at risk of death at the time of the event; it does not refer to an event which hypothetically might have caused death if it were more severe.

- Requires inpatient hospitalisation or prolongation of existing hospitalisation,
- Results in persistent or significant disability/incapacity, or
- Is a congenital anomaly/birth defect.

Other important medical events*

*Other events that may not result in death, are not life threatening, or do not require hospitalisation, may be considered a serious adverse event when, based upon appropriate medical judgement, the event may jeopardise the patient and may require medical or surgical intervention to prevent one of the outcomes listed above.

9.1.5 Expected Serious Adverse Events/Reactions

The patient cohort being studied are frail and have a high hospital readmission rate and mortality rate. For example in those with a diagnosis of COPD both national and local data suggest readmission to hospital will be 20% at one month, 33% at 3 months and 60% at one year. A number of these patients will be readmitted on more than one occasion (our study Greening N et al, BMJ 2014) demonstrated 599 hospitalisations in one year in a similar COPD population of 389. In addition mortality is expected to be 14% at 3 months and 20% at one year.

Given this is an observational study and the rates that are expected we would reasonably expect that hospitalisation or death are not routinely reported as SAEs (we would anticipated an excess of 600 SAEs if not). Therefore expected serious adverse events include (i) clinical deterioration and death of acutely breathless patients, (ii) adverse drug reactions to pharmacotherapy administered during the patients clinical care pathway, (iii) readmission to hospital for acute breathlessness due to acute exacerbations of comorbid conditions during the study period.

However, if any adverse events are experienced during any of the measures performed specifically related to research procedures (Table 1 and 2) e.g. breath sampling, administration of questionnaires, then these will be reported using the approved reporting procedure.

Page 31 of 46

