9.1.6 Suspected Unexpected Serious Adverse Reactions

A serious adverse reaction, the nature or severity of which is not consistent with the applicable product information

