9.3 Reporting Procedures for Serious Adverse Events

All SAEs, except those expected ones defined in section 9.1.5 that do not require immediate reporting (see 9.1.5), must be reported to the Sponsor within 24 hours day of discovery or notification of the event. The Sponsor will perform an initial check of the information and ensure that it is reviewed at the next R&D Management meeting. All SAE information must be recorded on an SAE form and sent to the Sponsor using the appropriate reporting form and the contact details on there. Additional information received for a case (follow-up or corrections to the original case) needs to be detailed on a new SAE form which must be sent to the Sponsor using the appropriate reporting form and the contact details on there. The Sponsor will report all SUSARs to the Research Ethics Committee concerned. Fatal or life-threatening SUSARs must be reported within 7 days and all other SUSARs within 15 days. The CI will inform all

In addition to the expedited reporting above, the CI shall submit once a year throughout the study or on request an Annual Report to the Ethics Committee which lists all SAEs / SUSARs that have occurred during the preceding 12 months.

investigators concerned of relevant information about SUSARs that could adversely affect the safety of

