15.2 Data Safety Monitoring Committee (DSMC)

The operations group within EMBER will report any unexpected serious adverse events to the core clinical group ([name], [name] [name] and [name]). All unexpected SAEs will be discussed by the core clinical group at monthly EMBER executive board meetings.

16.FINANCING AND INSURANCE

Direct Research Costs: Direct research costs required to deliver the stated research: including research staff, technicians, breath sampling, breath analysis and bioinformatics are fully funded by the UK Medical Research Council (MRC) and The Engineering and Physical Sciences Research Council (EPSRC) grant number MR/N005880/1. Additional funding has been received from the Midlands Asthma and Allergy Research Association (MAARA) and the Leicester National Institute for Health Respiratory (NIHR) Biomedical Researh Unit, for the EMBER clinical program.

NHS Treatment Costs: Not applicable for acute research studies as by definition patient care will often continue after the R&D activity has ceased due to the fact that patients will enter chronic care pathways.

NHS Support Costs: None anticipated as the research in question is a discovery biomarker campaign.

Insurance will be provided by the University of Leicester.

Page 38 of 46

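### A deterioration or death that follows a research procedure and is judged related to it carries no stated duty of prompt report to the sponsor

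*Protocol*

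**What the plan says.** Section 9.1.5 explains that the patients are frail, quotes high readmission and death rates in COPD, and concludes that "we would reasonably expect that hospitalisation or death are not routinely reported as SAEs". It then says that "expected serious adverse events include (i) clinical deterioration and death of acutely breathless patients". The other listed classes are adverse reactions to drugs given in the care pathway, and "readmission to hospital for acute breathlessness due to acute exacerbations of comorbid conditions during the study period". Reporting is restored only "if any adverse events are experienced during any of the measures performed specifically related to research procedures".

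Section 9.3 puts this into effect: "All SAEs, except those expected ones defined in section 9.1.5 that do not require immediate reporting (see 9.1.5), must be reported to the Sponsor", with a 24-hour limit. It has the sponsor send fatal or life-threatening SUSARs to the Research Ethics Committee within 7 days and other SUSARs within 15.

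Section 9.1.6 defines a SUSAR as a serious adverse reaction "the nature or severity of which is not consistent with the applicable product information". Section 15.2 provides that "All unexpected SAEs will be discussed by the core clinical group at monthly EMBER executive board meetings".

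Section 9.2 has every adverse event recorded on the CRF and its relationship to the study assessed by a medically qualified investigator.

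**The concern.** The exemption is defined by the kind of event, and nothing in it depends on cause. That suits background events: where death and deterioration are common, expediting each one would bury the sponsor in reports about the underlying disease. It does not suit the same kind of event when a study procedure may have caused it.

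Respiratory or cardiac deterioration is a plausible serious harm from a research procedure in an acutely ill, breathless patient, and it is also the listed type. If it appears some hours later, the provision that restores reporting does not reach it. At stake is whether the sponsor and the internal safety review learn promptly of a serious event that an investigator already believes the study caused.

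**Working it through.** No formula applies to the rule itself, so the sections are set side by side. The one linked figure is checked at the end.

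**Tracing one event.** Take a patient with acute breathlessness who deteriorates or dies some hours after a research procedure, where the investigator judges the event related.

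1. *Is it an expected SAE under 9.1.5?* Yes, by type. The class has no relatedness condition. The section heading covers reactions as well as events, and 9.1.2 defines reactions as study-related, so related events are not excluded by definition.
2. *Does the restoring provision apply?* No. It covers events during a measure, and this one came after.
3. *Must the investigator report it to the sponsor under 9.3?* No. The 24-hour rule excepts expected events as defined in 9.1.5, and no later report to the sponsor is described.
4. *Does the relatedness assessment in 9.2 change that?* No. It is recorded on the CRF, but nothing says that a related event loses the exemption.
5. *Does 15.2 pick it up?* Not on the 9.1.5 list, because only unexpected SAEs go to the core clinical group.
6. *Can the sponsor form its own view of causality, as 9.1.2 allows?* Only if it learns of the event.
7. *Is it a SUSAR?* Possibly. Section 9.1.6 compares the event with product information, not with the 9.1.5 list. The Synopsis states that there is no investigational medicinal product, and the protocol does not say which document serves for sputum induction, blood sampling or echocardiography. If the event counts as unexpected under 9.1.6, the sponsor owes the Ethics Committee a report within 7 days (fatal or life-threatening) or 15 days (otherwise). Section 9.3 meanwhile excuses the investigator from telling the sponsor. The two sections cannot both operate as written.

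**The burden figure.** Section 9.1.5 anticipates more than 600 SAEs without the exemption.

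- Hospitalisations in the cited COPD cohort: 599 in 389 patients over one year, or 599 / 389 = 1.54 per patient-year.
- Deaths at the stated one-year mortality of 20%: 0.20 × 389 = 78.
- Together: 599 + 78 = 677.

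The figure reproduces. It counts hospitalisations and deaths from all causes, so it supports not expediting unrelated background events. It does not bear on related ones.

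**The case against.** The strongest reply is that this is an observational study in standard care with no investigational product, that the exemption is reasoned, and that the events are not lost. Much of that stands.

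- *Never reported, or a signal that could not be seen.* A reader might infer this, but the protocol does not support it. Section 9.3 speaks of events not needing immediate reporting. The event goes on the CRF with a relatedness assessment (9.2), AE and SAE review is scheduled at visits 1b and 2 for acute patients (Tables 1 and 2), and the annual report to the Ethics Committee lists all SAEs. What is missing is a prompt route to the sponsor and to 15.2.
- *Cannot be a SUSAR.* This does not follow either, because 9.1.6 applies its own test. The supportable point is that the sections conflict.
- *All readmissions and all delayed harms escape.* They do not. The readmission class is limited by clinical cause, so a readmission attributed to a research procedure is not plainly inside it. Serious events outside the listed types stay reportable within 24 hours.
- *Induced sputum is a weak example.* In part. Section 6.1 plans spontaneous sputum, while Table 1 and the sputum text in 8.3 allow induction and anticipate a fall in FEV1. Induction in the acute phase is permitted but not clearly planned. The gap does not depend on it: breath sampling and blood sampling are also done in acutely ill patients. Section 7.3 excludes those in whom breath sampling is judged unsafe, which lowers the risk without supplying a reporting route.

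None of this closes the gap for a related deterioration or death that follows a procedure.

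**Conclusion.** The point holds in a limited form. For one class of event, the deterioration or death of an acutely breathless patient, the rule as written requires no prompt report to the sponsor when the event follows a research procedure and is judged related. Nor does that event reach the 15.2 review. Separately, 9.1.5, 9.1.6 and 9.3 disagree on what makes an event expected, so a SUSAR could be owed by a sponsor that need not have been told of it.

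The size cannot be put as a number. The protocol gives no rate of procedure-related serious events. Applying its COPD death and readmission rates to the cohort would count background events, almost all of them unrelated, and would not measure this gap.

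The conclusion rests on reading *during* literally and on the absence of any other stated route to the sponsor. It is worth correcting because it concerns participant safety and the judgement needed is already collected under 9.2.

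**What to change.** - **9.1.5 and 9.3:** limit the exemption to listed events that a medically qualified investigator judges not related to a research procedure.
- **9.1.5, restoring provision:** extend it from events during a research measure to events during it, or after it and suspected to be related to it.
- **9.1.6:** reconcile its reference for expectedness with 9.1.5, using a reference the study actually has. One option is the 9.1.5 list for unrelated disease events and a short list of foreseeable effects of each research procedure for related ones.

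Related events of the listed types then follow the 24-hour report, the SUSAR assessment with its 7- and 15-day limits, and the 15.2 review.

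The cost is wording in three subsections and one SAE form for each listed event judged related, which should be few. Unrelated background events stay exempt, so the concern about 600 SAEs is not reopened. Only reporting changes; clinical care does not.

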9.1.6 Suspected Unexpected Serious Adverse Reactions

A serious adverse reaction, the nature or severity of which is not consistent with the applicable product information

9.2 Reporting Procedures for All Adverse Events

All AEs occurring during the study observed by the investigator or reported by the participant, whether or not attributed to study, will be recorded on the CRF.

The following information will be recorded: description, date of onset and end date, severity, assessment of relatedness to study, other suspect device and action taken. Follow-up information should be provided as necessary

AEs considered related to the study as judged by a medically qualified investigator or the sponsor will be followed until resolution or the event is considered stable. All related AEs that result in a participant's withdrawal from the study or are present at the end of the study, should be followed up until a satisfactory resolution occurs.

It will be left to the investigator's clinical judgment whether or not an AE is of sufficient severity to require the participant's removal from the study. A participant may also voluntarily withdraw from treatment due to what he or she perceives as an intolerable AE. If either of these occurs, the participant must undergo an end of study assessment and be given appropriate care under medical supervision until symptoms cease or the condition becomes stable.

The severity of events will be assessed on the following scale: 1 = mild, 2 = moderate, 3 = severe. The relationship of AEs to the study will be assessed by a medically qualified investigator.

9.3 Reporting Procedures for Serious Adverse Events

All SAEs, except those expected ones defined in section 9.1.5 that do not require immediate reporting (see 9.1.5), must be reported to the Sponsor within 24 hours day of discovery or notification of the event. The Sponsor will perform an initial check of the information and ensure that it is reviewed at the next R&D Management meeting. All SAE information must be recorded on an SAE form and sent to the Sponsor using the appropriate reporting form and the contact details on there. Additional information received for a case (follow-up or corrections to the original case) needs to be detailed on a new SAE form which must be sent to the Sponsor using the appropriate reporting form and the contact details on there. The Sponsor will report all SUSARs to the Research Ethics Committee concerned. Fatal or life-threatening SUSARs must be reported within 7 days and all other SUSARs within 15 days. The CI will inform all

In addition to the expedited reporting above, the CI shall submit once a year throughout the study or on request an Annual Report to the Ethics Committee which lists all SAEs / SUSARs that have occurred during the preceding 12 months.

investigators concerned of relevant information about SUSARs that could adversely affect the safety of

10. STATISTICS

participants.

10.1 Description of Statistical Methods (Detailed statistical anad analytical methods are outlined in the MRC-EMBER data analysis plan).

Primary Analysis

For the primary analysis the outcome is a nominal variable with levels (1) Acute breathlessness (2) Recovery form acute breathlessness. The relationship between the primary outcome and the metabolomics biomarkers in exhaled breath sample will be modelled using multinomial logistic regression. Acute

Page 32 of 46

breathlessness will be defined as one or more of (i) patient defined acute breathlessness and/or a (ii) 1 unit increase in Extended Medical Research Council breathlessness score (eMRC). In addition to metabolomics markers the following independent variables will be included in the model: age, sex, standard acute care pathology markers blood eosinophils, BNP, CRP, Troponin-I, canonical VOCs extracted from breath analysis and where relevant validated co morbidity scores (e.g. Charlson comorbidity score).

Adjudication

All acute/healthy adult patients' notes will be sequentially divided. These will then be reviewed and independently adjudicated by two independent respiratory consultants, blinded to admission bloods and diagnosis. The panel will independantly decide the primary diagnosis as well as mark their level of certainty on a 100 mm VAS scale. The panel member will then be able to review imaging, ECGs, and ABGs but not blood results. Results will be both -validated by separate panel member to ensure agreement using Bland-Altman and Correlations and within rater agreement will be assessed by replicate analysis of at least 20 cases 4 weeks apart.

Binary logistic regressions will be utilised to assess associations between VOCs and acute disease. ROC curves will be produced for individual predictors in the primary analysis. Additional techniques for multi variate analysis including but not limited to cluster analysis, structural equation modelling and topological data analyses will be applied where relevant. Tables of descriptive statistics will be compiled for all key variables. All analysis will be performed using SAS 9.4 http://www.r-project.org/.

Secondary Analysis

For the secondary analysis pertaining to other definitions of acute breathlessness, visual analogue breathlessness scores (100mm) and a 1 unit increase in the extended medical research council analysis outlined above for the primary endpoint will be performed based upon stratification of breathlessness type.

For the secondary analyses pertaining to discovery of breath metabolomics markers the outcome is a nominal variable with levels (1) Acute Heart failure (2) Community acquired pneumonia 3) Adult exacerbations of asthma/COPD (both in combination and considered individually) and (4) Acute exacerbations childhood wheeze and confirmed asthma in children. The relationship between the primary outcome and the metabolomics biomarkers in exhaled breath sample will be modelled using multinomial logistic regression and ROC curves. In addition to metabolomics markers the following independent variables will be included in the models where necessary (improve model fit): age, sex, validated co morbidity scores such as the Charlson score, indicator disease risk scores such as the CURB-65 pneumonia score, DECAF COPD exacerbation scores and treatments commonly used acutely for the indicator diagnoses.

Subsidiary Analysis

For subsidiary analyses modelling risk of re admission, death and length of stay we will utilise the following approaches

- Cox proportional hazards model will be fitted and competing risk models will be fitted for readmission. Logistic regression analysis will be used when looking at risk at particular time points for readmission.
- The number of exacerbation events will be modelled using Poisson or Negative Binomial regression.
- Relationship between death and breath biomarkers will be evaluated using a logistic regression model.

Page 33 of 46

For subsidiary analyses pertaining to dynamic profile of breath biomarkers during (i) the acute states (time points 1a), (ii) transition to the stable state (time point 1b) and (iii) in the chronic state 8-12 weeks post exacerbation (time point 2), a repeated measures model with a random intercept and random effect for time will be fitted, the random effects will be fitted for each patient. For the repeated measures mixed model an unstructured covariance will be assumed.

Other outcomes are exploratory and based around feasibility of an acute care platform for airways disease. Statistical analyses for these outcomes will be performed as appropriate for hypotheses derived in this exploration.

